3.5 Stratification

The subjects will be sampled and stratified according to the following factors:

- 1) Age;

Seven (7) age groups: 50 - 54, 55 - 59, 60 - 64, 65 - 69, 70 - 74, 75 - 79, 80 or above;

- 2) Geographic region;

Five (5) regions in China: North, South, Southeast, Southwest, and Central

4 Variables and Epidemiological Measurements

All eligible participants will be included in the study to an endocrinologist, or other specialist, whenever appropriate, for the collection of all clinical and radiological information by 1 onsite study visit in a cross-sectional fashion. Spine radiograph and/or DXA may be separated from onsite interview by a follow-up visit as determined by the investigator.

Questionnaire

All demographic data, socioeconomic status, lifestyle information, and clinical features including medical history/concomitant medications, will be collected by an interviewer-administered questionnaire performed by the investigator. The questionnaire will be designed to adapt China's cultural and clinical practice. The analyzable variables derived from the questionnaire include (but not limited to):

- Age (absolute value and category);
- Place of birth and dwelling geographic region;
- BMI (height and weight, as measured in the site);
- Social status and lifestyle (educational level, occupation, monthly income, physical exercise, diet, smoking, alcohol intake, diet, calcium intake);
- Clinical features (age and years of menopause, medical history, history of osteoporosis and parental osteoporosis, any prior fractures, prior and concomitant medication, antiresorptive treatment, glucocorticoid treatment, other treatment reducing bone mass);
- FRAX score (as determined by self-reported fracture and radiology evidence and calculated based on the information from questionnaire with/without BMD).

BMD Measurement

The subject's densitometric measurement will be performed by DXA onsite. Different DXA scanners from manufacturers including Hologic, Lunar and Norland will be used onsite upon availability. The BMD of three skeletal locations, the lumbar spine, the femoral neck, and the total hip, will be determined and presented as absolute value, T-score. The definitions of normal (≥ -1.0 SD compared to young adult women), osteopenia (between -1 to -2.5 SD compared to young adult women) and of osteoporosis (≤ -2.5 SD compared to young adult women) will be applied for both locations in the study, by assessing densitometric readings based on the World Health Organization(WHO)classification [41]. Reference databases for the calculation of the T-score include the National Health and Nutrition Examination Survey (NHANES) III database for the hip and the manufacturer's database for the spine [42]. The US reference database in DXA devices provided by the manufacturers has been adopted in local China's clinical practice [3] and validated in published Chinese studies [36, 39]. No

single local reference database will be applied for a recalculation of T-score due to its relatively smaller sample size and lack of an extensive validation across Asian populations.

DXA has been established as a reliable method providing acceptable precision and accuracy. For lumbar spine, coefficients of variation (CV) in measurements have been reported between 0.26 and 1.5% in short-term studies [43-46], and between 0.8 and 2.6% in long-term studies [43-46]. Precision results for spine phantom measurements using DXA were reported between 0.4 and 0.67% and in long-term studies between 0.23% and 1.0% [43, 45-47]. The DXA measurement for the lumbar spine has a satisfactory diagnostic profile in terms of sensitivity and specificity (ROC AUC 94%) [45].

DXA Quality Control

All participating sites will be organized to have an investigator meeting at which principles and procedures for performing densitometry and densitometric analyses will be agreed for quality monitoring. Study and procedure training, for instance, patient positioning, will be provided for relevant site personnel. Day-to-day quality control will be executed by the participating site personnel. Measurement stability will be ensured by daily or alternate daily calibrations with brand-specific phantoms. The short-term measurement precision will be calculated based on individual site quality control program and alerted to the study team if coefficient of variation reaches 3.0%. Moreover, quality control in densitometry will be performed and enhanced by regular visits to sites by the Sponsor and its delegate. A periodic review of specimen analyses will be made by the investigators and the Sponsor.

DXA Machine and Cross-Calibration

DXA machines [Hologic (Waltham, MA, U.S.A.), Lunar (Madison, WI, U.S.A.), and Norland (Fort Atkinson, WI, U.S.A.)] in each site will be cross-calibrated for these beamed machines after observed BMD measurements are made. A two-step approach will be applied to calibrate BMD readings for all machines involved in the study. For each machine type in the study, the standardized BMD measurements will be derived from observed BMD in the manufacturer's own units using the equation by Pearson and colleagues [48] as below:

$$\text{Observed measurement} = \alpha * [1 - \exp(-\beta * \text{standardized BMD})] + \varepsilon_i$$

Where α is the asymptote and β is the slope when the standard BMD measurement is small. This curve-fitting formula was found by Pearson and colleagues to provide a better fit than the linear regression formula. When the exponential fit was employed the standardized BMD will be obtained by a re-arrangement to give:

$$\text{Standardized BMD} = \delta * \ln(\alpha) - \delta * \ln(\alpha - \text{Observed BMD})$$

Where $\delta=1/\beta$ and \ln is the natural logarithm.

This procedure will cross-calibrate machines of the same brand in the study. The second step is to cross-calibrate between brands to remove between-brand differences, by using equations developed by the International Committee for Standardization of Densitometry as following [47]:

Cross-Calibration for Lumbar Spine BMD

Hologic	= (0.906 * Lunar) - 0.025	= (0.912 * Norland) + 0.088
Lunar	= (1.074 * Hologic) + 0.054	= (0.995 * Norland) + 0.135
Norland	= (0.983 * Lunar) - 0.112	= (1.068 * Hologic) - 0.070

Cross-Calibration for Femoral Neck BMD

Hologic	= (0.836 * Lunar) - 0.008	= (0.836 * Norland) + 0.051
Lunar	= (1.013 * Hologic) + 0.142	= (0.945 * Norland) + 0.115
Norland	= (0.961 * Lunar) - 0.037	= (1.030 * Hologic) + 0.058

Alternatively, BMD cross-calibration may be made using other standards and equations, for example, European Spine Phantom prototype (ESPP) for spine [49] as well as the femoral neck and trochanter [50]. Cross-calibration results made by other standards and verifications for original calibrated results may be made and included in the statistical analysis plan (SAP) and clinical study report (CSR), if deemed necessary by the principal investigators and Merck's study team.

Vertebral Radiology

Lateral thoracic and lumbar spinal radiographs will be performed to assess any vertebral fractures in the study. The diagnosis of vertebral fractures will be standardized by the Genant semi-quantitative approach [51], based on recommendations of the International Osteoporosis Foundation. This visual method uses the qualitative features of vertebral shape and degree of reduction in vertebral height in the anterior, middle, or posterior vertical dimension to grade a vertebral body as normal, uncertain, or characterized by a mild, moderate, or severe fracture. The Genant's five grades for vertebrae T4 to L4 are listed as below:

- Grade 0 **normal**
Height of anterior, middle, and/or posterior is preserved;
- Grade 0.5 **borderline**

15-19.9% reduction in anterior, middle, and/or posterior height

- Grade 1 mild
20-25% reduction in anterior, middle, and/or posterior height and a reduction of area 10-20%
- Grade 2 moderate
25-40% reduction in any height and a reduction in area 20-40%
- Grade 3 severe
40% reduction in any height and area

In the study, vertebral fracture is defined as the presence of at least one vertebra morphometrically classified as grade 1, 2, or 3 on Genant's score as agreed by the both radiographic assessments in the study. Two (2) experienced radiologists who are blinded to the study will separately review the vertebral morphology and grade Genant's Score as per protocol. Radiologists will receive additional training to reduce variability between inter-observer interpretations. Prior to the study, each site will forward sample radiographs to the radiology coordination site for quality assessment and to check compliance with the protocol and technical standard. Intra- and inter-observer reliabilities will be tested using first 100 X-ray images from any study site before the adjudication starts. If there is a disagreement in terms of Genant's grading between two study radiologists, a third party radiological review will give a final decision.

The Genant semi-quantitative approach has been established a reliable and reproducible assessment in radiographic vertebral fracture. The intra-observer agreement for prevalent vertebral fracture was generally between 93 and 97% ($\kappa = 0.73 - 0.89$) [51], regardless of the radiologist's experience. As compared with reviewer's experience and other quantitative methods, an inter-observer agreement by difference in experience and method was between 92 and 94% ($\kappa = 0.65 - 0.74$) [51].

Definitions of Osteoporosis

In the study, osteoporosis is defined [3, 41] if the subject has at least one of the following as:

- A BMD T-score ≤ -2.5 in at least one of the anatomic sites including the lumbar spine, the femoral neck, and the total hip;
- A proven prior non-pathological fragility fracture.

A fragility fracture is defined as a fracture that occurred with minimal trauma at a typical site of osteoporotic fracture that would be unlikely to cause fracture in a non-osteoporotic adult. This assessment will be made based on self-reported fracture section included in the questionnaire and a review of medical history/documents/physical examination, or as suggested by the radiographic imaging in the study.

5 Study Flow Chart

Study Period:	Enrollment		Observation	Follow-Up
Visit Number/ Title:	Invitation#	Screening [△]	Study Visit**	Unscheduled Visit***
Study Day	NA	1	1	NA
Informed Consent		X		
Medical History [※]		X		
Inclusion/Exclusion Criteria		X		
Investigator-administered Questionnaire [¶]		X	X	
Physical Examination*				
DXA Measurement §			X	X
Spine Radiography &			X	X

#All available resources recording participant's demographic information will be used to randomly select invitees; a letter will be sent out to explain the study. The receipt and acceptance of invitation by the participant will be directly to the investigator; ^ informed consent, review of inclusion/exclusion criteria must be onsite, after the acceptance of study invitation from the participant; All eligible subjects will be allocated to a study ID number for all procedures;

** An onsite study visit will be conducted at the same day when the subject's eligibility to the study is determined.

*** An unscheduled follow-up may be performed by the investigator if the subject cannot have DXA measurement and/or spine X-ray on the study visit due to clinical and/or unexpected (i.e. DXA device failure) reason; ¶ A brief review of the subject's medical history, including menstrual history, physical ability and cognitive status will be performed to determine study eligibility at the screening;

¶ The questionnaire is an interview-based session administered by the investigator with Chinese official written language. Same individual investigator (s) will perform questionnaire interviews for all subjects at each study site. The questionnaire will collect self-reported data on demographics, gynecological history, socioeconomic status, life style factors, and clinical risk factors for osteoporosis. Standing height (centimeters) by a stadiometer and weight (kilograms) by a regularly calibrated scale will be determined at each site before the questionnaire;

* Include height and weight, and fracture-related physical examination;

§ Central DXA scanners from different manufacturers including Hologic, Lunar and Norland will be used to measure the BMD of the spine, the femoral neck, and the total hip. The subject's DXA measurement may be made on an unscheduled follow-up for any compelling reason (i.e. injected contrast material or device failure); & Two radiographies centered on T7 and L2 will be performed. Radiographs will be taken with the patient in the left lateral position and the subject will be required to breathe by instructions to allow blurring of the overlying ribs and lung detail by motion.

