6.1.2 Clinical Procedures/Assessments

6.1.2.1 Questionnaire and Physical Examination

The study's questionnaire will be developed based on questionnaires of previous large studies [29-34] and is attached in the Section 11 Appendices. During the investigator's meeting and training session, the questionnaire will be reviewed and discussed in order to clarify terms, country features, and standardization. The investigator will have training in understanding the questionnaire before the study enrollment. The questionnaire will be delivered by Chinese simplified written language. In order to minimize variability, it is preferred that the same individual investigator (s) perform questionnaire interviews for all subjects at each study site.

The questionnaire will collect self-reported data on demographics, gynecological history, socioeconomic status, life style factors, and clinical risk factors for osteoporosis. Commercial calcium supplement and vitamin D intake will be calculated according to names and daily doses reported by participants. Alcohol intake will be calculated in grams per day and be categorized according to the WHO as: never, for the subject who does not report alcohol intake; mild, from 1 to 10 grams per day; moderate, from 11 to 40 grams per day; and severe, for more than 40 grams per day. For smoking history, information on time and average number of cigarettes (and any other type of tobacco) consumed will be obtained. Physical activity will be assessed in minutes per day according to time spent on various activities including walking, dancing, and other Chinese specific outdoor activities.

All other major risk factors will be based on self-reported during the interview administered by the investigator. The subject's symptoms/signs and medical records will be reviewed for possible medical history. Comorbidities including asthma, chronic obstructive pulmonary disease (COPD), and diabetes mellitus are defined in the study (Refer to 'List of Definitions') and all definitions of diseases will be provided and further explained by the investigator during the interview. A detailed history of any fracture (after age of 40, anatomical site and the level of trauma) and height loss will be collected; prior and concomitant medications regarding steroids use, hormone replacement therapy (HRT), and any use of antiresorptive drugs will be recorded for medication name, daily dose and treatment duration.

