6.1.2.2 DXA Examination

All subjects are expected to have BMD measurement upon a successful completion of questionnaire. Densitometric measurement will be performed by a central dual-energy x-ray absorptiometry device at each site. DXA scanners from different manufacturers including Hologic, Lunar and Norland will be used onsite upon availability. A peripheral DXA on mobile health van must not be used in the study. BMD from all subjects included in a particular site will be measured by the same DXA machine or, at least, a machine from the same manufacturer. All BMD results from different machines will be quality controlled during the study.

On the day of the exam, the subject will be instructed to position and wear properly under a low X-ray radiation exposure. The subject will lie on a padded table, where legs will be supported on a padded box to flatten the pelvis and lumbar spine, and foot be placed in a brace that rotates the hip inward. Detailed positioning and other instructions will be suggested by the study DXA technicians according to the manufacturer's operation manual.

At the investigator's discretion, the subject's DXA measurement may be made on an unscheduled follow-up if there is any compelling reason (i.e. injected contrast materials or device failure) precluding the examination on the day of the study visit. The subject's BMD results from any institution 28 days prior to screening may be deemed appropriate for the study if such measurements are made per protocol as assessed by the investigator and discussed with the Sponsor. Subjects with known spine deformities will be required

to have densitometric measurement unless a waiver is made by the investigator after a consultation with the Sponsor.

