8.1.2.1 Prevalence of Osteoporosis

In the study, prevalence of osteoporosis in community-dwelling postmenopausal women in China will be investigated as a secondary objective. Descriptive statistics will be made to statistically address this objective. Point estimates (percentage) and corresponding 95% CI (exact binomial and Wilson score) will be presented for each analysis category and will be adjusted by age distribution in China [53]. Prevalence rates will also be given by age group and geographic region. A case with osteoporosis is counted based on the definition in Section 4.

The prevalence of osteoporosis will be presented as overall and by different diagnostic criteria and will be listed separately to allow an evaluation on the frequency distribution of each individual diagnostic setting in the study population.

The analysis of osteoporosis prevalence is displayed in the Table 8.1.2.1.

Table 8.1.2.1 Statistical Analysis Approaches on the Prevalence of Osteoporosis

Osteoporosis	Rate*	Estimate**	Frequency ***
Overall	Crude/Age-Standardized	Point and 95% CI	Percent
By DXA BMD [^]	Crude/Age-Standardized	Point and 95% CI	Percent
By Fragility Fracture [△]	Crude/Age-Standardized	Point and 95% CI	Percent & Cumulative

* Prevalence rates will be sub-analyzed by age group (50 – 54, 55 – 59, 60 – 65, 65 – 69, 70 – 74, 75 – 79, and 80+; and by < 65 and ≥ 65) and/or geographic region (North, South, Southeast, Southwest, and Central);
 ** Based on exact binomial distribution 95% CI and Wilson Score 95% CI;
 *** Calculation of frequency is relative to overall percent (100%);
 ^ the subject with a T-score ≤ -2.5 as suggested by a DXA measurement
 △ The subject with DXA measurement with a proven non-pathological major fracture as reported by the medical history or as suggested by radiology.

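### The osteoporosis prevalence rate has no place for women diagnosed earlier and treated who are now above -2.5 without a fragility fracture, so it understates the disease by an amount the documents do not fix

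*Combined protocol and SAP*

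**What the plan says.** Section 4 (Definitions of Osteoporosis) opens the case rule with "In the study, osteoporosis is defined [3, 41] if the subject has at least one of the following as", and two routes follow. One is by fracture history: "A proven prior non-pathological fragility fracture". The other is densitometric, and any one of three sites is enough: "A BMD T-score ≤ -2.5 in at least one of the anatomic sites including the lumbar spine, the femoral neck, and the total hip". Section 8.1.2.1 ties the prevalence analysis to that rule: "A case with osteoporosis is counted based on the definition in Section 4". The DXA row of Table 8.1.2.1 is footnoted as "the subject with a T-score ≤ -2.5 as suggested by a DXA measurement".

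The T-score is a current one. It is measured at the study visit or an unscheduled visit, or taken from a recent scan: "The subject's BMD results from any institution 28 days prior to screening may be deemed appropriate for the study" (6.1.2.2). An older diagnostic T-score has no standing.

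Previous diagnosis and treatment are nevertheless collected. Section 4 (Questionnaire) lists "history of osteoporosis and parental osteoporosis, any prior fractures, prior and concomitant medication, antiresorptive treatment" among the analysable variables, and 6.1.2.1 adds that "any use of antiresorptive drugs will be recorded for medication name, daily dose and treatment duration". The same section provides for review of medical records. Section 8.1.4 summarises prior and concomitant therapies descriptively, and under 8.1.2.2 clinical parameters may enter the logistic models. Neither step changes who is counted as a case. The exclusion criteria (3.4) do not name treated women, and the limitations (8.2.3) do not mention them.

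**The concern.** Secondary objective 1 is the prevalence of osteoporosis, without the word densitometric; secondary objective 3 does use that word. The definition is also not a pure statement of current bone density, because a proven fragility fracture makes a woman a case whatever her BMD is now. An earlier DXA diagnosis followed by treatment gets no equivalent recognition. The plan does not say how such women are meant to count.

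The effect on the disease rate can only be downward, and it grows with treatment coverage. The rate is to be shown by age group and region. If coverage differs between regions, part of any regional difference will reflect care already received rather than how common the disease is.

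**Working it through.** **The plan's own figures.** The rows of Table 8.3.1 sum to 44 + 81 + 100 + 90 + 80 + 70 + 53 = 518. Allowing for 5% withdrawal, 518 / 0.95 = 545.3, against 545 stated per region. Five regions give 5 × 545 = 2725, against about 2700 stated. The sample size reproduces and is not in dispute. It serves here only to scale the bias. With 5% lost, n = 0.95 × 2700 = 2565 (the plan states the 5% for radiographs; applying it to DXA is an assumption).

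**Assumptions, none of them in the documents.** The lowest-site T-score without treatment is N(-1.9, 1.1). Between 5% and 20% of women at or below -2.5 are treated. Treatment raises the T-score by d = 0.3 to 0.5.

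**Untreated prevalence.** Φ((-2.5 + 1.9)/1.1) = Φ(-0.545) = 29.3%. Section 1.1 cites 27.3% for Chinese women aged 50 or above, so the assumed distribution is of the right order.

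**Share of treated cases now above -2.5.** [Φ(-0.545) - Φ((-0.6 - d)/1.1)] / 0.293:
- d = 0.3: (0.293 - 0.207)/0.293 = 0.29
- d = 0.5: (0.293 - 0.159)/0.293 = 0.46

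**Points missed** = treated share × 29.3% × share crossing:

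| Share of cases treated | d = 0.3 | d = 0.5 |
|---|---|---|
| 5% | 0.4 | 0.7 |
| 10% | 0.9 | 1.3 |
| 20% | 1.7 | 2.7 |

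**Yardstick.** The simple binomial 95% half-width is 1.96 × √(0.293 × 0.707 / 2565) = 1.8 points. For one region, with 2565/5 = 513 women, it is 1.96 × √(0.293 × 0.707 / 513) = 3.9 points. Neither allows for the sampling design.

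**Factors that shrink the bias.**
- If treatment goes preferentially to women with lower T-scores (assumed weight exp(-T)), the share crossing falls from 29-46% to 14-24%. At 10% treated, the loss is then 0.10 × 29.3 × 0.14 to 0.24 = 0.4-0.7 points.
- Treated women with a fragility fracture, including one seen on the study radiograph, are still counted. If 15-30% of treated women have one (assumption), the 10% row becomes 0.6-1.1 points.

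**A second parameterisation.** Take 27.3% as the true rate, with 5-30% of cases treated and 10-50% of those lost to the count (assumptions). The missed share m is 0.5-15%, and the bias 27.3 × m is 0.14-4.1 points, or about 4 to 111 of 2700 women. The exact 95% half-width at 27.3% and n = 2700 is 1.70 points. The bias reaches that when m = 1.70/27.3 = 6.2%.

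**Effect on comparisons.** Give two groups the same untreated prevalence of 29.3%, with 20% against 5% of cases treated. Observed prevalence is 27.6% against 28.8% (d = 0.3), or 26.6% against 28.6% (d = 0.5). The odds ratios are 0.94 and 0.90 from treatment alone. With 15% against 5% treated and d = 0.4, the odds ratio is 0.95.

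**The case against.** The definition is explicit, sourced and used consistently in the List of Definitions, Section 4 and 8.1.2.1. Counting women who currently meet criteria, rather than those ever diagnosed, is a legitimate choice of estimand. This stands as a reason to keep the current rate. It does not remove the gap, because the fracture limb already departs from current BMD status and the plan does not say which estimand is meant for treated women.

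A reader might go further and infer that treated women contaminate the control group of the 8.1.2.2 densitometric model. The documents do not support that. The outcome there is densitometric osteoporosis, a T-score state, and a woman above -2.5 at all three sites is correctly a control for it. Treatment has altered her outcome; the study has not misclassified it. Case status in the vertebral-fracture model is not affected at all. It follows that removing treated women from the controls alone would be wrong: every remaining treated woman would be a case, and the antiresorptive variable could not be estimated.

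A reader might also infer that income, education or region will look materially protective. The shift for a factor with no true effect is only about 0.90-0.95, and then only under an assumed three- to fourfold difference in treatment coverage. Nothing in the documents shows such a difference, or high coverage anywhere.

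Finally, the documents do not require proof of an earlier diagnosis. Much of the history is self-reported with record review, and earlier scans need not meet the study's reference-database or central-DXA rules. This limits what an added row can claim, but is no reason to omit it.

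**Conclusion.** The point holds for prevalence. As a measure of osteoporosis as a disease, the 8.1.2.1 rate is biased downward whenever there are previously diagnosed, treated, unfractured women now above -2.5 at all three sites, and nothing in the plan detects or reports them. The direction follows from the definition. The size does not: 0.4-2.7 points under the main assumptions, 0.14-4.1 under wider ones, and toward the lower end if treated women have lower T-scores or fractures. At 5-10% treated, the bias lies inside the overall half-width of 1.8 points; only at about 20% does it reach or exceed it. For a single region it stays below the 3.9-point half-width throughout the main range.

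For the densitometric model the point is narrower: the outcome is correctly classified but modified by treatment, which calls for a sensitivity analysis and does not show an error. This is an inexpensive improvement to a secondary objective, and leaves the primary objective untouched.

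**What to change.** 1. **8.1.2.1 and Table 8.1.2.1.** Keep the present rate as the main result. Add a supplementary row, overall and by age group and region, that also counts any woman with a previous osteoporosis diagnosis (from the questionnaire history and medical-record review) plus current or past antiresorptive treatment. State that the main rate describes women currently meeting the T-score or fracture criteria.
2. **8.1.2.2.** Add a sensitivity fit of the densitometric-osteoporosis model that excludes all women with current or past antiresorptive treatment, cases and controls alike.

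**Cost.** This needs SAP wording, one table row and one extra model fit. Section 8.1 says a separate SAP is still to be written, so it can go there. No new visit or measurement is needed, although how well an earlier diagnosis is documented will vary.

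**Downside.** Some earlier diagnoses may not meet the study's T-score standard, so the row should be read as an upper companion to the main rate, not a replacement. The sensitivity fit loses some women and describes untreated women only. If the two rates agree, the report can say that the issue is immaterial.

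### The plan has no rule for removing fractured lumbar vertebrae from the lumbar T-score, so lumbar BMD is likely to read high in women whose fracture lies in the scanned levels

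*Combined protocol and SAP*

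**What the plan says.** Section 4 (BMD Measurement) states: "The BMD of three skeletal locations, the lumbar spine, the femoral neck, and the total hip, will be determined". It does not list the lumbar levels. Section 4 (Definitions of Osteoporosis) requires a T-score of -2.5 or lower "in at least one of the anatomic sites including the lumbar spine", the femoral neck and the total hip, so a lumbar value alone can classify a woman.

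Section 4 (Vertebral Radiology) introduces the fracture reading with "The Genant's five grades for vertebrae T4 to L4 are listed as below". It defines grade 1 as "20-25% reduction in anterior, middle, and/or posterior height and a reduction of area 10-20" percent and grade 2 as "25-40% reduction in any height and a reduction in area 20-40" percent. The graded range therefore overlaps the lumbar spine, and the grades carry explicit losses of area.

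The only provision for abnormal spines is in Section 6.1.2.2: "Subjects with known spine deformities will be required" to undergo densitometry "unless a waiver is made by the investigator after a consultation with the Sponsor". The waiver is not limited to the spine scan.

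Section 8.1.2.2 fits BMD in the risk-factor models as a continuous and also as a dichotomous variable, without naming a site. Section 8.1.3 has a logistic model relating adjudicated fracture to densitometric osteoporosis. Section 8.1.4 rules out imputation for study variables.

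**The concern.** Areal BMD is mineral divided by projected area. If a vertebra loses area and keeps its mineral, its BMD goes up although the bone is no stronger. A lumbar value that includes such a level is too high, and this happens only in women with a lumbar fracture. The error therefore runs in one direction and is tied to the outcome of the fracture model.

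Three results could be affected: the By DXA BMD row of Table 8.1.2.1, any lumbar BMD term in the fracture model, and the Section 8.1.3 logistic model on densitometric osteoporosis. Making BMD dichotomous, which Section 8.1.2.2 does because of collinearity, would not remove the error.

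The deformity provision does not close the gap. It applies only to known deformities, and Section 1.1 says that most vertebral fractures go undiagnosed. Where the waiver is used as written, hip BMD may be lost too. With no imputation, a likely fracture case then drops out of every BMD analysis.

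**Working it through.** **Size of the fracture group.** The documents give no figure for lumbar BMD error, so only the sample size can be reproduced. The age-group sizes in Table 8.3.1 sum to 518. Allowing for 5% withdrawal, 518/0.95 = 545.3, which matches the stated 545 per region, and 5 × 545 = 2725 against approximately 2700. The prevalence in that table, weighted by group size, is 85.98/518 = 16.6%. That is about 430 fracture cases among 5 × 518 = 2590 evaluable women.

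**Rise in lumbar BMD.** Let one of four scanned vertebrae of equal area lose a fraction r of its area and keep its mineral. The rise is 1/(1 - r/4) - 1. The values of r come from the protocol's grade definitions. Four levels, equal areas and unchanged mineral are assumptions.

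**Shift in T-score at the threshold.** Let the young-adult SD be a fraction c of the young-adult mean, with c assumed to be 0.10 to 0.12. At T = -2.5, BMD is (1 - 2.5c) of that mean, so the shift is (1 - 2.5c) × rise / c.

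| Area loss r | Rise in lumbar BMD | T shift, c = 0.12 | T shift, c = 0.10 |
|---|---|---|---|
| 10% | 2.6% | +0.15 | +0.19 |
| 20% | 5.3% | +0.31 | +0.39 |
| 40% | 11.1% | +0.65 | +0.83 |

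For scale, Section 4 (DXA Quality Control) alerts the study team when the short-term coefficient of variation reaches 3.0%. That is a limit on random precision and not on bias, but the shift is of similar size or larger.

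**Effect on the analyses.** This was simulated with 1,000,000 women per scenario. Assumptions not in the documents: lumbar T mean -1.8, SD 1.3; one hip site with T mean -1.6, SD 1.1; correlation 0.6; c = 0.11; true odds ratio (OR) for fracture 1.60 per SD lower lumbar BMD. Fracture prevalence was set to 16.6%. The share of fracture cases with one scanned lumbar fracture was varied from 20% to 60%, and r from 10% to 40%. Each cell gives the value with fractured levels excluded, then included.

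| Share, r | T ≤ -2.5 at either site, all women | Same, fracture cases | OR, densitometric osteoporosis and fracture | OR per SD lower lumbar BMD |
|---|---|---|---|---|
| 20%, 10% | 37.04% → 36.92% | 50.6% → 49.9% | 1.96 → 1.90 | 1.60 → 1.55 |
| 40%, 20% | 37.09% → 36.63% | 50.9% → 48.1% | 1.98 → 1.77 | 1.60 → 1.43 |
| 60%, 40% | 37.11% → 35.87% | 50.9% → 43.4% | 1.98 → 1.46 | 1.60 → 1.12 |

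Overall densitometric prevalence falls by 0.12, 0.46 and 1.24 points. If every adjudicated fracture counts as a fragility fracture, composite osteoporosis is the same with and without exclusion in each scenario, at 45.2-45.3%.

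**The case against.** The strongest reply is that the protocol never says fractured levels are kept. Section 4 (DXA Quality Control) provides for a meeting at which "principles and procedures for performing densitometry and densitometric analyses will be agreed for quality monitoring", Section 6.1.2.2 refers positioning and other instructions to the manufacturer's manual, and Section 8.1 promises a separate SAP. A rule could come from any of these. This stands in part: inclusion is inferred from silence. But no rule is written. Sites use different manufacturers, so unwritten handling could differ by site and hence by region. Exclusion decided at the site would also rest on onsite reading, whose accuracy Section 2.3 sets out to test.

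The geometry is also open to challenge. The grades are read on lateral films, while the DXA positioning in Section 6.1.2.2 points to a frontal scan. A wedge that loses anterior height and keeps posterior height need not lose the same fraction of frontal area. This stands, so the tabulated rises suit uniform collapse and are too large for wedges. A reader might also put height loss into the formula and start the range at 20%, a rise of 5.3%. The protocol gives area loss separately, from 10%, so the low end is 2.6%.

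The consequences are limited as well. Section 8.1.2.2 names no BMD site, and hip BMD would not carry this error. Either of two hip sites can classify a woman, whereas the simulation has only one, so the offset may be larger than shown. The sensitivity and specificity analysis in Section 8.1.3 uses the study's osteoporosis diagnosis as truth; only the logistic model that follows uses densitometric osteoporosis. All of this stands.

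**Conclusion.** The point holds as a missing rule with a likely one-directional error, and it is minor. The lumbar T-score can classify a woman, the study's own reading identifies fractured lumbar levels, and nothing written links the two. In women with a fracture in a scanned lumbar level, lumbar BMD is likely to be raised by up to about 2.6-11%, or +0.15 to +0.8 T-units. That range rests on one of four levels being affected, uniform collapse, unchanged mineral and an assumed young-adult SD. Several fractured lumbar levels would enlarge it; wedging or mineral loss would shrink it.

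In the assumed scenarios, the main effect is on lumbar BMD as a risk factor, where the OR per SD falls from 1.60 to between 1.55 and 1.12. Densitometric prevalence moves by only about 0.1-1.2 points.

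A reader might infer that lumbar BMD is inflated in all fracture cases and that osteoporosis prevalence is seriously understated. The documents do not support this. Thoracic fractures do not alter lumbar BMD, and Section 1.1 places most fractures in the midthoracic region or the thoracolumbar transition zone. Composite osteoporosis is largely protected because a fracture seen on study imaging can itself qualify. The primary endpoint, vertebral fracture prevalence, does not use BMD.

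The loss of hip BMD through the waiver cannot be sized, because the documents give no expected number of waivers.

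**What to change.** In the SAP:

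- Name the lumbar levels analysed.
- Derive lumbar BMD and T-score without any level of adjudicated grade 1 or more.
- Set a minimum number of evaluable levels, and classify on the hip sites when fewer remain.
- Name the BMD site in the Section 8.1.2.2 models. Use a hip site as the BMD term in the fracture model, or at least as a sensitivity analysis.
- Report the all-vertebrae lumbar result as a sensitivity analysis.

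In Section 6.1.2.2, limit the waiver to the spine scan so that hip BMD is still measured.

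The cost is re-analysis of existing scans in women with a lumbar fracture, and some missing lumbar values. There is also a methodological price. Cases would be measured on fewer lumbar levels than non-cases, and the re-analysis would not be blind to fracture status. The hip-only analysis checks both, because it needs no vertebral exclusion.
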